4.1. Sample size calculation

In order to note a 40% difference in the postprandial response of triglycerides and/or LDL-cholesterol and in order to have an 80% chance of a statistically significant difference between the studied groups at a significance level of 5%, a necessary sample of 10 subjects was calculated.

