2.2. Study Objectives / Research Questions

Purpose

The purpose of this study was the investigation of the postprandial responses on serum total, HDL-, LDL- cholesterol, triglycerides, uric acid, glucose and plasma Total Antioxidant Capacity (TAC), after the intake of a traditional, Authentic Ladotyri Mytilinis cheese, compared to corresponding responses after an Italian Parmesan cheese consumption, in healthy participants.

Research Questions

The research questions of this clinical study are the following:

- ✓ Which is the acute effect of ALM-PDO cheese consumption, in the framework of a high-fat and carbohydrates meal, on the postprandial biomarkers of lipemia, glycemia and oxidative stress?
- ✓ Does the postprandial inflammatory and metabolic responses to ALM-PDO cheese differs, compared to Italian Parmesan PDO cheese? LDL- cholesterol and triglycerides determined at 3h after the meal intake, was set as the primary endpoint of the present, pilot study.

3. Summary presentation / study design

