3.1. Overview

A nutritional intervention – clinical study of self-comparison design (cross over design: acute study) will take place in a sample of healthy volunteers, where the difference in the effectiveness of the nutritional intervention will be evaluated in the same volunteer. This means that the response of lipemia, glycemia and oxidative stress biomarkers to the intervention meal will be compared with their response to the control meal, in the same volunteer each time. The specific research will be carried out in the specially designed area of

the Human Nutrition unit of the University of the Aegean and in collaboration with the hospital of Lemnos, with which a collaboration protocol has been concluded with the University of the Aegean.

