After a seven-day washout period, on the eighth day (2nd test period) the same participants will be asked to come again, in a fasting state, to the specially designed area of the University of the Aegean, at the predetermined morning hours to repeat the procedure nutritional intervention and blood sampling. In other words, a blood sample will be taken by a doctor or competent staff of the Limnos Hospital, followed by a discussion with the volunteer and completion of a 24-hour recall of food consumption questionnaire. The questionnaire that the participants will complete at the start of the second test period is to record their specific eating habits during the washout period (ie the interval between the two periods of the intervention). The meals served to the volunteers are determined by the control or intervention group to which they belong. After each meal is consumed within the 15-min timeperiod, subsequent blood sampling will be done for participants 30, 90, and 180 minutes (min)after the completion of the meal .

4. Enrollment of participants and case of study withdrawal

The goal is to gather an initial sample of people from the Greek area in order to achieve the collection of a required number of cases for study. The research team will then review the inclusion/exclusion criteria and select the participants who will receive the meals in the two test periods of the study.

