6.3. Statistical analysis

After the above analyzes have been carried out using a special biochemical analyzer, the use of the statistical package SPSS (Statistical package for social sciences: SPSS) will follow in order to record, process and analyze the results of the study. The Kolmogorov–Smirnov test was applied to check normality. The main participants' characteristics will be analyzed by descriptive statistics. Differences in baseline values between groups for each biomarker tested, will be analyzed using a paired sample two tailed t test. Repeated ANOVA measures with Geisser–Greenhouse correction will be conducted, for serum total, HDL-, LDL- cholesterol, triglycerides, glucose, uric acid and plasma Total Antioxidant Capacity (TAC). If time or group was significant, multiple comparison post hoc Bonferroni test will be performed for the comparison of concentrations. To check changes in the metabolic biomarkers from baseline to postprandial responses (within-group variation), the Wilcoxon sign-rank test will be carried out.

7. Maintenance of study records

The study files will remain securely registered for a maximum of 3 years from the date of their registration in special areas of the Human Nutrition Unit, University of the Aegean. Study records should be kept for a maximum of 2 years after the last marketing approval, or longer if required by local regulations.

8. Ethics, Consent and Privacy Statement

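### Two primary markers share one 5% level and one 80% power, with no rule on whether one or both must succeed and no test tied to the 3 h comparison

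*Combined protocol and SAP*

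**What the plan says.** All references are to the combined protocol and SAP.

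- **Section 2.2** sets the endpoint: "LDL- cholesterol and triglycerides determined at 3h after the meal intake, was set as the primary endpoint of the present, pilot study". That is two markers at one time point, described as a single endpoint.
- **Section 4.1** aims to "note a 40% difference in the postprandial response of triglycerides and/or LDL-cholesterol and in order to have an 80% chance" of a significant result, and continues: "significance level of 5%, a necessary sample of 10 subjects was calculated". One level, one power and one sample size serve both markers. No SD, sidedness or test is given, and 3 h is not mentioned.
- **Section 3.1** makes the comparison within person: "the difference in the effectiveness of the nutritional intervention will be evaluated in the same volunteer". **Section 3.2** has a fasting sample and then "subsequent blood sampling will be done for participants 30, 90, and 180 minutes" after the meal, so there are four times per visit.
- **Section 6.3** assigns the two-tailed paired t test to baseline values and the Wilcoxon test to change within each group. Repeated-measures ANOVA with Geisser-Greenhouse "correction will be conducted, for serum total, HDL-, LDL- cholesterol, triglycerides, glucose, uric acid and plasma Total Antioxidant Capacity (TAC") covers seven biomarkers, none marked as primary. Then: "If time or group was significant, multiple comparison post hoc Bonferroni test will be performed for the comparison of concentrations". The section mentions neither the primary endpoint, nor 3 h, nor a cheese-by-time term, nor any adjustment across LDL-cholesterol and triglycerides.

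**The concern.** Two things are left open.

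**The success rule.** With two markers joined by and/or, success could mean that either marker is significant or that both are. These are different hypotheses. Under the first, two chances at 5% give more than a 5% risk of a false primary claim. Under the second, that risk is held, but both tests must succeed, so joint power is below a per-marker 80%. One stated 5% and one stated 80% cannot describe both.

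**The test.** After baseline, section 6.3 offers one between-cheese route: ANOVA, then a Bonferroni step. An overall group effect averages over the sampling times, so it is a different claim from a difference at 3 h. The post hoc step can open on a time effect alone, which a meal can produce when the cheeses do not differ. The comparisons over which Bonferroni is applied are not listed.

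What is at stake is that the rule and the test could both be settled after the results are known. The reported 5% and 80% would then have no fixed meaning.

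**Working it through.** **1. Can the plan's figure be reproduced?** No. n = 10 needs an SD for the within-person difference, and none is stated. It can only be back-solved. For a two-sided paired t test,

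power = P(|T| > t(1 - α/2; n - 1)), with T noncentral t, df = n - 1, noncentrality dz × √n.

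With n = 10, α = 0.05 and power 80%, dz = 0.996. A 40% difference then implies an SD of 40 / 0.996 = 40.2 points. Under the same test, an SD of 30, 40, 50 or 60 points would need 7, 10, 15 or 20 subjects. So n = 10 is attainable, but cannot be checked.

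**2. Assumptions for the rest (not in the documents).** Two-sided paired t test; n = 10; each marker alone has 80% power at 5% (dz = 0.996); correlation between the two markers' within-person differences from -0.5 to 0.9.

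**3. Either marker suffices, each at an unadjusted 5%.** Independent markers: 1 - 0.95² = 9.75%. With both effects real and independent, the chance of at least one finding is 1 - 0.20² = 96%.

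**4. Both markers required, each at 5%.** Error is at most 5%. Joint power for independent markers is 0.80² = 64%.

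Simulation over the assumed correlations (400,000 runs):

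| Correlation | -0.5 | 0 | 0.5 | 0.8 | 0.9 |
|---|---|---|---|---|---|
| Either at 5%: false claim | 9.2% | 9.7% | 9.1% | 8.0% | 7.2% |
| Either at 5%: at least one true finding | 98.2% | 96.0% | 92.0% | 87.7% | 85.4% |
| Both at 5%: joint power | 61.8% | 64.0% | 68.1% | 72.4% | 74.5% |

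**5. The ANOVA and Bonferroni route.** Section 6.3 does not define the set of comparisons, so no single figure applies. Per-marker power at the same dz, ignoring the ANOVA gate, depends on what one supposes:

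| Supposed set of comparisons | Level per comparison | Power |
|---|---|---|
| Cheeses at 3 h only (1) | 0.05 | 80% |
| Cheeses at three post-meal times (3) | 0.05/3 | 60.0% |
| Cheeses at all four times (4) | 0.05/4 | 54.3% |
| All pairs of four times (4 × 3 / 2 = 6) | 0.05/6 | 46.5% |
| All pairs of eight cheese-by-time cells (8 × 7 / 2 = 28) | 0.05/28 | 22.1% |

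Two-marker error moves with it: about 7-10% with one comparison, about 2.6-3.3% with three, about 2.0-2.5% with four. On this route error and power cannot be determined from the plan.

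**6. Cost of a defined rule, same assumptions.** Under a fixed sequence the first marker keeps 80%, and the second has the joint power in step 4. Under Holm at n = 10, per-marker power is 73-77% if both effects are real and about 68% if only one is. If both are required, joint power is 77-84% at n = 12 and 82-88% at n = 13. At a level of 0.025, per-marker power is 79.0% at n = 12 and 83.2% at n = 13.

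**The case against.** The best defence has three parts.

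- **A route exists.** Section 6.3 applies ANOVA with a post hoc comparison to both primary markers, so it would be too strong to say that they have no between-cheese analysis. That stands. What fails is the link from that route to the 3 h endpoint.
- **Section 2.2 joins the markers with and.** This can be read as requiring both, which would hold error at 5%. Section 4.1, with its and/or, prevents that reading from being definitive.
- **It is a pilot.** This lowers the stakes. It does not settle the rule, because 4.1 makes a formal 5% and 80% claim.

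A reader might also infer more than the documents support:

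- **That the trial's type I error is inflated, or that its 5% and 80% are wrong.** The inflation follows only if either marker suffices at an unadjusted 5%, and the plan does not choose that rule.
- **That the Bonferroni step runs over the sampling times**, so that error is below 5% and power is 54-60%. Section 6.3 does not say so, and with one comparison there would be no loss.
- **That only the per-marker reading can yield 80%.** That would assume its own conclusion: the sponsor's 80% may have been calculated for either marker or for both jointly.
- **That 10 subjects are too few.** Without an SD this cannot be shown.

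**Conclusion.** The concern holds as an undefined decision rule for two primary markers, together with a between-cheese analysis that is not tied to 3 h. It goes beyond missing detail, because the and/or wording with no control across markers permits a false-claim rate of about 7-10% (9.75% if independent), while the both-required reading gives joint power of about 62-75% if 80% is a per-marker figure. The directions are general: short of perfect correlation, testing either marker at 5% raises error above 5%, and requiring both puts joint power below a per-marker 80%. The sizes rest on the assumptions in step 2 of the working. The adequacy of n = 10 remains unjudged. This should be fixed; severity is modest given the pilot status in 2.2.

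**What to change.** Before any data are seen, state one decision rule in the same words in 2.2, 4.1 and 6.3.

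- **Rule.** One option is a fixed sequence: the sponsor names the first marker, which is tested at two-sided 5%; the other is tested at 5% only if the first is significant. Holm across the two, or a both-required rule, is equally acceptable. Each holds 5% over the pair.
- **Variable and test.** For each marker, name one primary variable, either the 3 h concentration or the 3 h change from baseline, so that 2.2 and 4.1 agree. Name one two-sided within-person between-cheese test of it at 3 h, done whatever the ANOVA shows and kept outside the post hoc Bonferroni.
- **ANOVA.** Keep it and its post hoc step as secondary analyses.
- **Power.** In 4.1, restate power for the chosen rule from the sponsor's own within-person SD for each marker. The percentages here are illustrative and should not be copied into the protocol.

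**Cost.** Wording in three sections and one recalculated power figure. A fixed sequence allows no claim on the second marker if the first fails, but needs no extra participants for the first marker if its SD supports 80%. Holm or both-required means a lower stated power at n = 10. Under the illustrative assumptions, keeping 80% would take about 12-13 participants if both are required, and 13 under Holm if only one effect is real.

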4.2. Study inclusion criteria

The criteria that must be met by those interested in conducting the study are the following:

- Age between 18 and 65 years
- Willingness to join and complete the nutritional intervention
- There should be no history of loss of consciousness in previous blood draws as well as personal reasons for not being able to donate blood (e.g. fear)
- Who will sign a written consent to participate in the study

4.3. Exclusion criteria from the study

Participants meeting, at baseline, the following exclusion criteria will be excluded from the study for reasons of safety as well as efficacy of the study:

- ✓ Inability or unwillingness to provide informed consent
- ✓ Age <18 and >30 years
- ✓ Three-month nutritional supplement
- ✓ Chronic diseases history
- ✓ Hemoglobin A1c - HbA1c > 5.7 %
- ✓ Abnormal Body Mass Index (BMI) (> 25 kg / m²)
- ✓ Abnormal hematological or bio-chemical profile (total cholesterol > 240 mg/dL, triglycerides > 250 mg/dL, glucose > 100 mg/dL)
- ✓ Alcohol overdose (> 40 g alcohol / day)
- ✓ Heavy smokers (> 10 cigarettes / day)
- ✓ Concurrent participation in another intervention study or unconsciousness in previous blood draws

4.4. Strategy for participant inclusion and retention

Finding the study participants will be done by the University and/or the wider local community of Lemnos. The volunteers will be either students or members of the teaching staff of the University of the Aegean or residents of the island. One of the members of the research coordinators will undertake the briefing of each healthy volunteer, which will take place in a special area of the University. Those who will meet all the criteria of the study in order to be accepted and at the same time agree in writing to participate in it, on the days that they will come to this special area, they will have the possibility at any time to ask for help either from the main researcher or from anyone else research representative to record any difficulties or questions they may have. The members of the research team will be responsible for timely

informing the participants, in writing or by telephone, of the visits and the biological samples to be collected.

The scientific manager of the study or his representatives will be responsible for the safekeeping of the data and results. The anonymity of the participants will be preserved and the safe keeping of the history of the healthy will be ensured, to which only the personnel who will be employed in this research will have access.

4.5. Participant withdrawal criteria

Participants are free to withdraw from the study at any time. Accordingly the researcher will be able to ask the participant to leave the study if:

- o Clinical adverse events, laboratory abnormality, or other medical condition or condition are identified that endanger the participant from remaining in the study
- o Participants meet one of the aforementioned exclusion criteria (either newly developed or not previously identified) that precludes further participation in the study
- o Participants appear to not adequately adhere to protocol requirements

4.6. Suspension or early termination of the study

This study may be suspended or terminated early only if there is sufficient cause. A written notice documenting the reason for stopping or suspending the study will be provided by the person responsible for this decision (research team, hospital).

5. Study Intervention

5.1. Description of intervention

As part of a meal that will include two slices of bread of 80 grams (g), and a glass of 250 ml of water, the control group will consume two pieces of Italian parmesan cheese (PDO), total weight of 100 grams (g), while the intervention groups will consume corresponding bread meal, where the control cheese will be replaced with 100 grams (two pieces) of Authentic Ladotyri Mytilinis cheese (PDO). The meals will be prepared at the Nutrition and Public Health laboratory of the Human Nutrition Unit, University of the Aegean.

For the selected foods, there does not seem to be any data suggesting that they may have a possible risk or negative impact on health, as on the one hand there is no confirmed adverse effect of its individual components on health based on the scientific literature and on the other hand it appears according to corresponding research in similar foods the potential beneficial role of their biofunctional components in health promotion.

5.2. Assessment of participant compliance for administration

The assessment of the compliance of the participants in the study with regard to the administration of cream cheese, will be achieved following continuous supervision by a member of the research team, of the volunteers who will come to the University site to consume all the meals.

6. Study Procedures

6.1. Questionnaires

A specially designed questionnaire, based on bibliographic data, will be used to collect important data regarding the participants of the study.

The questionnaire will concern the clinical condition and habits (especially nutritional) of the volunteers of the clinical study and will include the following parts:

1st part

General socio-demographic and anthropometric data of the study population (gender, age, anthropometric indicators)

2nd part

Clinical status of each participant (medication, dietary supplements, etc.).

3rd part

Dietary and other habits before the start of the intervention, as well as more specific dietary habits for the washout period.

6.2. Biological samples

The collection of blood samples, by a doctor or competent staff of the Limnos Hospital, of the healthy volunteers of the clinical study will be used to determine indicators of postprandial lipemia, glycemia and oxidative stress in the blood (plasma antioxidant capacity, lipid profile specifically triglycerides, HDL & LDL cholesterol, glucose, etc.) that will be analyzed using a special biochemical analyzer.

6.3. Statistical analysis

After the above analyzes have been carried out using a special biochemical analyzer, the use of the statistical package SPSS (Statistical package for social sciences: SPSS) will follow in order to record, process and analyze the results of the study. The Kolmogorov–Smirnov test was applied to check normality. The main participants' characteristics will be analyzed by descriptive statistics. Differences in baseline values between groups for each biomarker tested, will be analyzed using a paired sample two tailed t test. Repeated ANOVA measures with Geisser–Greenhouse correction will be conducted, for serum total, HDL-, LDL- cholesterol, triglycerides, glucose, uric acid and plasma Total Antioxidant Capacity (TAC). If time or group was significant, multiple comparison post hoc Bonferroni test will be performed for the comparison of concentrations. To check changes in the metabolic biomarkers from baseline to postprandial responses (within-group variation), the Wilcoxon sign-rank test will be carried out.

7. Maintenance of study records

The study files will remain securely registered for a maximum of 3 years from the date of their registration in special areas of the Human Nutrition Unit, University of the Aegean. Study records should be kept for a maximum of 2 years after the last marketing approval, or longer if required by local regulations.

8. Ethics, Consent and Privacy Statement

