3.2. Study design

In a total sample of approximately 10 healthy volunteers, the number of which was determined through a special statistical program for calculating the required sample of the research to draw safe and reliable conclusions, a nutritional intervention – clinical study of cross-over design will be carried out. The study for each participant will be 7 days long, including the washout period.

Each participant during the first test period and in a state of 12-hour fasting, will be asked to come in the morning hours of 9 am. - 12:30 p.m., the specially designed blood collection room of the Human Nutrition Unit, Department of Food Science and Nutrition, University of the Aegean. In this specially designed area, a blood sample (baseline) will be taken by a doctor or competent staff of the Lemnos Hospital. This will be followed by a discussion with the healthy volunteer, signing of a declaration of participation, filling in a questionnaire and a 24-hour recall of food consumption. The questionnaire that each volunteer will fill out on the first day of the start of the study concerns their medical history and general information about their habits (especially dietary). Afterwards, a meal will be served that will include 2 slices of bread (80g- 40g each) and 2 pieces of cheese (100g- 50g each piece), according to the group each volunteer belongs to, accompanied in each case by 1 glass of water. The consumption of each meal will be completed within the time period of 15 minutes by all participants (controlled). Finally, the following blood samplings will be carried out for the volunteers, which will be conducted 30 minutes, 1.5 and 3 hours after the completion of the meal.

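### If meal and time are both within-person factors, the planned repeated-measures ANOVA discards a participant's two observed 3 h primary values whenever a fasting, 30-min or 90-min sample is missing

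*Combined protocol and SAP*

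**What the plan says.** Section 2.2 fixes the endpoint at one time point: "LDL- cholesterol and triglycerides determined at 3h after the meal intake, was set as the primary endpoint". Section 3.2 has a fasting sample at each visit, and after the meal "subsequent blood sampling will be done for participants 30, 90, and 180 minutes" later. That makes four samples per meal and eight per person. Section 3.1 says the two meals are to be compared within the same volunteer.

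For postprandial values, section 6.3 plans one between-meal method, run in SPSS: "Repeated ANOVA measures with Geisser–Greenhouse correction will be conducted, for serum total, HDL-, LDL- cholesterol, triglycerides, glucose, uric acid" and plasma antioxidant capacity. Bonferroni comparisons follow if time or group is significant. The paired t test in 6.3 is for baseline values, and the Wilcoxon test is for change from baseline within a group.

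Section 4.1 states that "a necessary sample of 10 subjects was calculated", and 3.2 repeats the figure as approximate ("In a total sample of approximately 10 healthy volunteers"). Section 4.5 adds that "Participants are free to withdraw from the study at any time". No section gives a rule for missing samples, an analysis set, a replacement rule or an allowance for loss.

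**The concern.** A classical repeated-measures ANOVA with a sphericity correction works on a complete row of repeated measures for each person. With meal and time both within-person, the row has eight cells. One empty cell removes the person from the analysis of that biomarker.

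The primary question needs only two of those cells, the 3 h value under each meal. Someone whose 30-min tube fails but who has both 3 h results has everything the primary comparison needs, yet is left out. With 10 people, each such exclusion costs a tenth of the sample for that biomarker. It also limits the result to people with a full set of eight samples. Nothing else in 6.3 brings those values back into a comparison of the meals.

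**Working it through.** **Inputs from the documents.** 10 people, 80% power, 5% significance, a 40% difference (4.1); eight samples per person (3.2); endpoint at 3 h (2.2); within-person comparison (3.1).

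**Inputs assumed.** The documents give no SD and no rate of missed samples. I take a two-sided test and an independent miss probability q per draw of 0.5%, 1%, 2% or 5%.

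**Step 1: the plan's figure of 10.** The target is stated as "In order to note a 40% difference in the postprandial response of triglycerides and/or LDL-cholesterol". Without an SD the figure cannot be reproduced, so I solve for what it implies. For a paired t test, power(n) = P(T > t with 0.975 and n − 1 df), where T is noncentral t with noncentrality d√n (the opposite tail is negligible). Setting power(10) = 0.80 gives d = 0.996, so the implied SD of the within-person difference is 40 / 0.996 = 40.2%. Assumed SDs of 20, 30, 40, 50 and 60% would need 5, 7, 10, 15 and 20 people. Ten is therefore consistent with an SD near 40%, but the documents do not confirm it.

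**Step 2: what each lost person costs.** At d = 0.996, power is 80.0% with 10 people, 74.5% with 9, 67.7% with 8 and 59.7% with 7.

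**Step 3: that the method drops the row.** I simulated 10 people with two meals and four times in a balanced repeated-measures routine (not SPSS itself). With one 30-min value removed, the routine refused to run. With that person removed it ran; error df fell from 9 to 8 for meal and from 27 to 24 for time, and two observed 3 h values were lost.

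**Step 4: how often, and at what cost.** The share of people with all eight samples is (1 − q)^8; the share with both 3 h samples is (1 − q)^2. The chance that at least one of 10 is lost is 1 − share^10. Average power is the sum over k of Binomial(k; 10, share) × power(k).

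| q per draw | All 8 present | Both 3 h present | At least 1 of 10 lost: 8 needed / 2 needed | Average power: 8 needed / 2 needed |
|---|---|---|---|---|
| 0.5% | 96.1% | 99.0% | 33% / 10% | 77.7% / 79.4% |
| 1% | 92.3% | 98.0% | 55% / 18% | 75.4% / 78.9% |
| 2% | 85.1% | 96.0% | 80% / 33% | 70.5% / 77.7% |
| 5% | 66.3% | 90.3% | 98% / 64% | 55.2% / 74.1% |

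Example at 2%: 0.98^8 = 0.851 and 0.98^2 = 0.960.

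**Step 5: if the 3 h value is analysed as change from fasting.** Four samples are then needed. At q = 2% and 5% the shares are 0.98^4 = 92.2% and 0.95^4 = 81.5%, and average power is 75.4% and 67.8%. The gap narrows but remains.

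**Step 6: is a mixed model a safe replacement?** I simulated 10 people with complete data, no meal effect and residual SD 1, and fitted a participant random effect only. With a visit-level SD of 0.5 or 1.0, the meal main effect was rejected in about 14% or 27% of runs at nominal 5%, and the 3 h contrast in about 6% or 8%. A paired 3 h comparison stayed at 5%.

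**The case against.** **The deletion is inferred.** Section 6.3 does not mention complete cases and does not define its factors. It speaks of time and group, and the protocol uses group labels for the two meals. If group were entered as a between-person factor, a missed draw would remove only that visit's record. This stands as a condition on the point. That model would, however, ignore the within-person pairing that 3.1 makes the basis of the comparison, so 6.3 would need correcting anyway.

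**Other tests can still use the data.** Deletion is per biomarker, and the Wilcoxon tests can use the remaining baseline-to-3 h pairs. True, but they do not compare the meals. The Bonferroni comparisons are conditional on the ANOVA, and 6.3 does not say that they use a wider set of people.

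**Losses may be rare or clustered.** Sampling is on site by hospital staff, meals are supervised, and people with problems at earlier blood draws are screened out (3.2, 4.2, 4.3, 5.2). At 0.5% per draw the power gap is under two points. If people miss whole visits, both rules lose the same people and there is no gap. This stands: the 5% row is the upper end of an assumed range, not a forecast.

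**The power figures are not for the ANOVA.** Both columns use a paired t test on 3 h values at a back-solved effect. They measure the cost of losing people, not the power of the ANOVA's own tests.

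**Withdrawal.** A reader might infer from 4.5 that leaving mid-visit also throws away observed primary values. The documents do not support this. The 3 h draw is the last of each visit, so leaving during visit 1 leaves no 3 h value. Leaving during visit 2 leaves one, which a paired 3 h comparison cannot use either and a mixed model would recover only in part.

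**Conclusion.** The point holds in a conditional and limited form. With meal and time within-person, the only planned between-meal analysis excludes people whose primary 3 h values were both observed, because of samples that the primary comparison does not need. No other section prevents it.

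The power cost runs from under two points at an assumed 0.5% per draw to about 19 points at 5% (74.1 − 55.2). It rests on independent misses, a two-sided paired t test and an effect back-solved to 80% power with 10 people. It vanishes if samples are lost only by whole visit. The documents support neither a particular miss rate nor a claim about withdrawals. The change is still worth making: a trial of 10 with no stated allowance for loss has little room, and the remedy needs no new data.

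**What to change.** In 6.3, define the primary comparison of LDL-cholesterol and of triglycerides at 3 h as a paired within-person analysis. It should include every participant with a 3 h value under both meals, whatever happened at the other draws. State whether the 3 h value is analysed as measured or as change from fasting; if the latter, both fasting samples are also required. State the factors of the ANOVA if it is kept for the time course.

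If a mixed model replaces the ANOVA for the time course, fit it to all available samples with:

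- meal, time, meal-by-time, period and sequence as fixed effects;
- random effects for participant and for visit within participant, or an equivalent within-visit covariance;
- a small-sample degrees-of-freedom correction.

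A participant random effect alone is not enough, as step 6 of the check shows. The cost is revised wording and a little more analysis work; no extra samples or participants are needed.
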